7 OBJECTIVES AND HYPOTHESES

The hypothesis of the study is that DDD pacing with CLS stimulation is able to overcome the cardioinhibitory reflex with DDD pacing and to counteract, at least in part, the vasodepressor component of the reflex - which is usually associated in tilt-positive patients- with CLS activation. The study hypothesis is that DDD pacing with CLS stimulation is able to prevent syncopal recurrence completely or partially by transforming syncope in pre-syncope.

7.1 Objectives

7.1.1 Primary objectives

The study has the primary objective of comparing time to first syncopal recurrence between

- active group (CLS): CLS in addition to DDD pacing mode; and
- control group (CTL): sensing only, ODO mode.

Definition. According to the 2009 ESC guidelines⁽⁷⁾, a syncopal recurrence is defined as a transient complete loss of consciousness characterized by rapid onset, short duration, and spontaneous complete recovery.

7.1.2 Secondary objectives: clinical outcome

The Secondary endpoint will be the time to the first recurrence of pre-syncope or syncope, whichever comes first, compared between the study groups during follow-up

Definition. Pre-syncope is defined as any of the various signs and symptoms which are recognized by the patients as premonitory of imminent syncope but not followed by syncope.

7.2 Primary hypotheses

7.2.1 Comparison of syncope survival rate during 2-year follow-up

Null: the 2-year survival rate of syncopal recurrence in the treatment arm (S_{CLS}) is equal to the 2-year survival rate of the control arm (S_{CTL}), assuming an exponential distribution with proportional hazard rates.

$$H_0: S_{CLS}(t=2 \text{ years}) = S_{CTL}(t=2 \text{ years})$$

Alternative: the 2-year survival rate of syncopal recurrence in the treatment arm is different from the 2-year survival rate of the control arm.

$$H_1: S_{CLS}(t=2 \text{ years}) \neq S_{CTL}(t=2 \text{ years})$$

7.3 Secondary hypotheses

7.3.1 Comparison of pre-syncope or syncope survival rate during 2-year follow-up

Null: the 2-year survival rate to the combined event of pre-syncope or syncope, $\Sigma(t)$, is equal in both study groups

$$H_0: \Sigma_{CLS}(t=2 \text{ years}) = \Sigma_{CTL}(t=2 \text{ years})$$

Alternative: the 2-year survival rate to the combined event of pre-syncope or syncope is different in the two study groups.

$$H_1: \Sigma_{CLS}(t=2 \text{ years}) \neq \Sigma_{CTL}(t=2 \text{ years})$$

7.4 Safety assessments

All Adverse Events (AE) and Adverse Device will be reported and documented and risk analysis will be constantly updated throughout the study.

An independent DSMB will be monitoring the study conduct reviewing all available source document related to any death occurring during the study and recommending early study termination, if deemed appropriate.

Should a patient in ODO mode study arm die, source document review will be performed immediately, without any undue delay as soon as all relevant documents are available

8 DESIGN OF THE CLINICAL INVESTIGATION

8.1 General considerations

The study is a prospective, multi-center, double-blinded, randomized, intention-to-treat, placebo-controlled study.

8.2 Endpoints

8.2.1 Primary endpoint

The Primary Endpoint will be the time to the first post randomization recurrence of a syncopal episode as defined in Section 7.1.1.

8.2.2 Secondary endpoints

The Secondary endpoint will be the time to the first post randomization recurrence of a pre-syncope or syncope episode (as defined in Section 7.1 and 7.1.2.1), whichever comes first.

8.3 Measures taken to minimize or avoid bias

8.3.1 Randomization

Patients will be randomized to the active group or to placebo immediately after their enrolment and before any subsequent study-related procedure.

- Active group: before post-implant hospital discharge, IPG will be programmed in a dual-chamber DDD pacing mode with the CLS function ON, and according to the programming recommendations reported in section 9.4.
- Control group: before post-implant hospital discharge, pacing will be programmed in the ODO mode, according to the programming recommendations reported in section 9.4.

Randomization ratio will be 1:1, therefore the randomization procedure will ensure that each individual patient will have (approximately) 50% chance to be assigned to the active group or to the control.

A centralized block-randomization procedure will be used. Block size will vary from 2 to 4 and investigators will not be aware of randomization block sizes at any time. Randomization will not be stratified.

Randomization will be communicated with an online procedure: investigators will connect to a dedicated webpage of the electronic Case Report Form (eCRF).

8.3.2 Blinding

Patients will be blinded to the treatment assignment until the end of the study or the first endpoint event.

Investigators will not be blinded to the randomizations but they will not assess the primary endpoint events.

The primary endpoint events will be collected by dedicated patients' self-administered structured questionnaire. Responses to the questionnaire will determine whether or not the event description and the associated symptoms are consistent with a primary endpoint event.

Questionnaires will be anonymous, identified by the patient ID study code, and provided to patients at enrolment. Questionnaires will be prepared upfront in 8 pre-paid envelopes (additional backup questionnaires may be provided) addressed to an external contract research organization (CRO), whose personnel will remain blinded both to patients' identity and randomization assignment.

8.3.3 Primary and clinical secondary endpoint assessment

At enrolment, participating subjects will be instructed on how and when to fill in and mail the questionnaires to the CRO.

A questionnaire will be completed by the patient him-/herself at home separately after each single experienced syncope or pre-syncope event. Every 3 months starting from enrolment date patients will mail the collected questionnaires to the CRO using the pre-paid and pre-addressed envelopes provided at enrolment. If a patient will not experience any syncopal or pre-syncopal event during a 3-month period, he/she will complete a single questionnaire documenting the absence of any recurrence.

Patients will be instructed to mail only anonymous questionnaires and envelopes.

CRO personnel will monitor the timing of questionnaire flow. In case of delays, the CRO staff will inform the investigator, who will contact the patient to solicit the questionnaire or to fix any related problems. The CRO will also inform the investigators about the occurrence of a syncope or pre-syncope event.

Responses to the questionnaire will determine whether or not the event description and the associated symptoms are consistent with a primary or secondary endpoint event.

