6.3 Steps to control or mitigate the risks

As reported in the Risk Analysis and in the IB the following measures will be adopted to mitigate the risks associated with the participation in the study.

Clinical Investigation Plan and Study Design shall include:

- 1) An independent DSMB will be monitoring the study conduct reviewing all available source document related to any death occurring during the study and recommending early study termination, if deemed appropriate.
- 2) Should a patient in ODO mode study arm die, source document review will be performed immediately, without any undue delay as soon as all relevant documents are available
- 3) The following procedures have been introduced in the study CIP:
 - Subjects terminate study participation at the first adjudicated syncope recurrence
 - Three interim analysis are planned to early terminate the study in case of evidence of superiority of the treatment arm
 - independent DSMB to periodically monitor the study status and preliminary results, recommending termination in case of unacceptable risk
 - Investigators are allowed to take any medical decision deemed appropriate, including pacemaker reprogramming
 - Advice the patient to avoid activity which may pose risks in case of transient loss of consciousness
- 4) The password/code is communicate only to hospital staff involved in the study after appropriate training
- 5) Resuscitation equipment available during pacemaker setup
- 6) The following measures must be taken during a TT:
 - a pacemaker programmer available in the room and switched on before the test starts
 - Adherence to current guidelines
 - Use of nitroglycerine
 - Resuscitation equipment available during tests
- 7) Initial training and, if necessary, periodic re-training of the hospital study staff

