9.6 Primary endpoint collection

Self-administered anonymous patient questionnaires will be collected every 3 months after post-implant hospital discharge (within a ± 14 day interval) by independent personnel of a CRO as described in section 8.3.3.

Syncope and pre-syncope assessment will be exclusively based on what patients will refer by self-administering the questionnaire, at home, separately for each event.

Despite patients will be instructed to fill in the study questionnaire, they might react differently to a syncope recurrence during the study. The following Table 4 reports the most awaited situations and illustrates the subsequent steps accordingly.

Table 4. After a syncopal and pre-syncopal recurrence

| Situation: | The patient fills in the questionnaire | The patient shows up for a medical examination |
|------------|---|---|
| 1 step | The CRO quarterly collects patient questionnaires | The investigator recommends the patient to mail the questionnaire to the CRO in due time and reports any AE |
| 2 step | If an AE occurred, the CRO informs the investigator | |

Any change of the programmed pacing mode not justified by a primary endpoint (even when a-posteriori assessed), will be considered as a crossover, but analyzed according to the Intention-To-Treat (ITT) principle, see Section 11)

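### Quarterly mailing keeps a clear-cut syncope from the CRO for about 46 days on average, and delays the formal exit that Protocol 6.3 lists as a risk mitigation

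*Protocol*

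**What the plan says.** The form is filled in promptly. Protocol 8.3.3: "A questionnaire will be completed by the patient him-/herself at home separately after each single experienced syncope or pre-syncope event". It is not sent promptly: "Every 3 months starting from enrolment date patients will mail the collected questionnaires to the CRO". Protocol 9.1 and SAP 4.4 repeat the three-month mailing. Protocol 9.6 has the forms collected "every 3 months after post-implant hospital discharge (within a ± 14 day interval"), and Table 4 again gives quarterly collection as the first step. The supply fits one mailing per quarter over 24 months: "Questionnaires will be prepared upfront in 8 pre-paid envelopes" (Protocol 8.3.2), with backup questionnaires possible.

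Nothing else feeds the assessment: "Syncope and pre-syncope assessment will be exclusively based on what patients will refer by self-administering the questionnaire" (Protocol 9.6).

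Exit depends on that assessment. Protocol 8.8.6 ends participation at the 24-month visit or once a primary event has been assessed. Protocol 4.5.1 keeps ODO mode active until the first adjudicated recurrence, the end of follow-up or withdrawal. Protocol 9.5.5 requires ODO to be switched off at the termination follow-up. Protocol 6.3 counts the exit among its risk controls: "Subjects terminate study participation at the first adjudicated syncope recurrence". Protocol 6.4 credits placebo patients with access to pacing after their first primary event.

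On notice to the site, Protocol 8.3.3 says "The CRO will also inform the investigators about the occurrence of a syncope or pre-syncope event", while Table 4 says "If an AE occurred, the CRO informs the investigator". If the patient comes to the clinic instead, Table 4 has the investigator advise posting the form in good time and report any AE.

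**The concern.** The chain is episode, form, mailing, receipt, assessment, exit. The plan makes the second step immediate and the third quarterly. This applies to every syncope, including those that need no adjudication, and so is separate from the batching of unclassified episodes in Protocol 9.9.

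At stake is the match between the data flow and the risk-benefit text. A control patient who has already reached the primary endpoint contributes nothing more to the primary analysis. Yet if that patient only fills in the form and does not come to the site, the exit that 6.3 and 6.4 rely on starts only after the mailing.

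Trial conduct is affected too. Protocol 11.7.1 has the CRO report event counts monthly, but the forms behind them arrive quarterly. Protocol 9.9 limits each interim analysis to events collected when adjudication is called, so recent events still at home are left out.

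**Working it through.** The documents state no reporting delay, so the delay has to be derived.

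**Inputs**
- Mailing interval: 3 months, T = 365.25/4 = 91.3 days (Protocol 8.3.3, 9.6).
- Collection window: ±14 days (Protocol 9.6).
- Two-year incidence: 57% control, 34% active, exponential times (Protocol 11.2; SAP section on sample size).
- Control arm: 64 patients, 10% loss (Protocol 11.2).

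**Check of the hazards against the plan's own figure**
- Control: -ln(1 - 0.57)/2 = 0.422 per year.
- Active: -ln(1 - 0.34)/2 = 0.208 per year.
- Ratio: 0.208/0.422 = 0.49, the hazard ratio that the plan states.

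**Time the form is held at home**
- Mean, with events spread evenly over the quarter: T/2 = 45.7 days.
- Mean with exponential first-event times at the plan's rates: 46.5 days (control), 46.1 days (active).
- Mean with each mailing shifted at random within ±14 days: 46.6 days.
- Longest wait if mailed on the due date: 91.3 days.
- Longest wait at the late edge of the window: 91.3 + 14 = 105.3 days.
- Longest wait if the previous mailing was 14 days early and the next 14 days late: 91.3 + 28 = 119.3 days.
- Share held for more than 30 days: 1 - 30/91.3 = 67%.

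Postal transit and assessment time come on top. The documents give neither.

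**Further syncopes during the wait, control arm**
- First events without loss: 64 × 0.57 = 36.5.
- With 10% loss over two years, the loss hazard is -ln(0.9)/2 = 0.053 per year. The event probability is 0.422/(0.422 + 0.053) × (1 - exp(-2 × 0.475)) = 0.545, and 64 × 0.545 = 34.9, or about 35 events.
- Mean wait: 45.7/365.25 = 1/8 year.
- Expected further syncopes: 35 × 0.422 × 1/8 = 1.8, or about 2.
- For one control patient, the chance of a further syncope in 46 days is 1 - exp(-0.422 × 46/365.25) = 5.2%.

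This takes the plan's first-recurrence hazard as unchanged after the first event, and assumes that no patient is reprogrammed in the meantime.

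**Is there a faster route?** None appears in the protocol or SAP. Home Monitoring is recommended, not required (Protocol 9.1.1), and 9.6 excludes any basis for assessment other than the questionnaire. The CRO chases overdue mailings (8.3.3), but only once they are overdue.

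**The case against.** The strongest reply is that only the formal exit waits. Protocol 6.3, in the same list, lets investigators take any medical decision, including reprogramming. Protocol 9.6 foresees a mode change justified by an endpoint that is confirmed only afterwards, and does not then count it as a crossover. Protocol 9.5.4 allows unscheduled visits at any time. This stands. A reader might infer that a control patient cannot be helped until the form arrives, and the documents do not support that. The gap concerns patients who complete the form and do not come in, which is the first situation in Table 4.

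Other inferences also go too far:
- **Late SAE reporting.** Site reporting does not run through the questionnaire. Protocol 18.8 sets 24 hours from detection and has the investigator obtain information from family and other hospitals.
- **A flat contradiction between Table 4 and 8.3.3.** A spontaneous syncope is an adverse event under Protocol 18.1, which exempts only uncomplicated events during the 1-month tilt test. The two passages can be read together, so the mismatch is mainly one of wording.
- **Bias or lost events.** The endpoint is time to the episode and the form is completed per episode, so late mailing does not shift event times. The documents give no rate of lost forms. Chasing would, however, not reveal one missing form inside an envelope that did arrive.
- **About 9 further syncopes.** Using 2 per year gives 35 × 2/8 = 8.8. That rate is the pre-enrolment threshold for inclusion, not a post-randomization rate in the plan.

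Finally, SAP 7.5 refers to a separate charter for questionnaire collection and adjudication, which was not available. It may contain a faster route.

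**Conclusion.** The point holds as a data-flow weakness that is cheap to correct. As the protocol and SAP are written, a clear-cut syncope stays unknown to the CRO for about 46 days on average, and up to about 119 days if each mailing is within its window, plus transit. For patients who do not present, the exit credited in 6.3 and 6.4 starts only after that. Event counts and interim triggers lag in the same way. The expected clinical size on the plan's own hazard is small, about 2 further syncopes across roughly 35 control events.

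The figures assume that patients keep to the mailing schedule and that first events follow the plan's exponential model. The conclusion does not extend to bias in the primary analysis, nor to any claim that care is unavailable during the wait.

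**What to change.** In Protocol 8.3.3, 9.1 and 9.6 and SAP 4.4, have patients mail any form that reports a suspected or uncertain loss of consciousness promptly, for example within 3 working days, in a spare pre-paid envelope. The CRO assesses it and notifies the site on receipt. All other forms stay quarterly. Holding time for these forms then falls from about 46 days on average to a few days. Transit is added in either case; the documents give no figure, and 3 to 7 days is an assumption.

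Also:
- Align the Table 4 wording on notice to the investigator with 8.3.3.
- Reconcile the start of the quarters, which is enrolment in 8.3.3 but discharge in 9.1, 9.6 and SAP 4.4.
- Reconcile the mailing and exit passages with 6.3 and 6.4.
- If the questionnaire charter already has a faster route, state it in the protocol.

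What is done clinically after the notice is left to the sponsor.

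The cost is at least 128 spare envelopes, because each patient must hold one before an event, plus a revised instruction sheet and CRO handling on receipt. The patient and CRO blinds are unaffected. One limit remains: a syncope that the patient takes for pre-syncope would still wait for the quarterly mailing, which is why the instruction should include uncertain episodes.

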8.4 Methods

8.4.1 eCRF

All parameters and measurements that are recorded within the study are described in this section and are documented on the appropriate eCRFs.

The corresponding time schedule is described in Section 9.

- Enrollment Form
- Baseline Form
- Implantation Form
- Pre-Hospital Discharge Form
- In-hospital Follow-up Form for 1- (optional), 12-, 24-month follow-up visits, as well as interim visits.
- Patient's self-administered questionnaire
- Adverse Event/Device Deficiency Form
- Study Termination Form

8.5 Equipment to be used for the assessment of variables

Implanted device and related equipments and accessories are described in Section 4.3.

In addition, at investigator's discretion, selected patients may undergo TT exam before and during study participation (1-month after discharge). This test will require the use of standard CE-marked equipments, such as TT tables and related tools to electronically record continuous data on BP and heart rate.

8.6 Replacement of subjects

The sample size is calculated in consideration of an expected dropout rate. Therefore it is not planned to replace subjects.

However a patient undergoing a surgical implant revision (implying skin incision for pocket and lead position revision) before the 1-month follow-up, will continue his/her study.

8.7 Used devices and comparators

8.7.1 Description of exposure to the investigational device and/or comparator

All patients are exposed to the investigational devices Eluna 8, Epyra 8, Etrinsa 8 IPGs as described in Section 4.3.

8.7.2 Justification of the choice of comparators

The comparator is the same investigational device programmed in the ODO mode. Justification is given in section 3.1.

8.7.3 List of any other medical device and/or medication to be used during the investigation

In addition to the investigational device, the following devices, tools and accessories may be used during device implantation and follow-up:

- Threshold analyzer;
- RENAMIC programmers or later models;
- Implant accessory kits

The remote monitoring system, namely BIOTRONIK Home Monitoring (HM), is recommended during the study. The HM enables automatic daily transmissions from the implant to a patient unit (CardioMessenger) which forwards diagnostic, therapy and device data to Service Center (SC). Data resident in the SC are available to the attending physician by connecting to a secure web page.

As per clinical practice, selected patients will undergo TT exam before and, optionally, at 1-month follow-up during study participation. This test will require the use of standard CE-marked equipments: TT tables and CE-marked devices to electronically record continuous data on blood pressure (BP) and heart rate.

Such devices must be available at the investigational sites before study participation and will not be provided by the Sponsor.

8.7.4 Number of investigational devices to be used and a justification

Within the study, 128 Eluna 8 DR(/-T/ProMRI), Epyra DR-T(/ProMRI), Etrinsa DR-T(/ProMRI) IPGs will be used.

Justification is given in Section 11.

8.8 Subjects

8.8.1 Description of patient population

Patient selection adheres to the class IIB indication for cardiac pacing of the guidelines of the European Society of Cardiology⁽¹⁾.

8.8.2 Inclusion criteria

Patients affected by clinical diagnosis of reflex (neurally-mediated) syncope who meet all the following criteria:

- age ≥ 40 years
- significant limitation of social and working life due to unpredictable frequent syncope recurrences, ≥ 2 of which within the last year.
- type 2B cardio-inhibitory response (VASIS classification) during TT performed according to the 'Italian protocol'.^(7, 17)
- alternative therapies have failed or were not feasible.
- exclusion of other possible competitive causes of syncope.

8.8.3 Exclusion criteria

- Any classified indication to pacemaker different from reflex syncope with positive Tilt Test response
- Any classified indication implantable defibrillator (ICD), cardiac resynchronization therapy (CRT), according to current guidelines
- Any cardiac dysfunctions likely leading to loss of consciousness:
 - overt heart failure;
 - ejection fraction (LVEF) $< 40\%$ (Echo-assessed within 3-month prior to study participation);
 - myocardial infarction;
 - diagnosis of hypertrophic or dilated cardiomyopathy;
 - clinically significant valvular disease;
 - sinus bradycardia < 50 bpm or sinoatrial block;
 - Mobitz I second degree atrioventricular block;
 - Mobitz II second or third-degree atrioventricular block;
 - bundle-branch block;
 - rapid paroxysmal supraventricular tachycardia or ventricular tachycardia;
 - pre-excited QRS complexes;
 - prolonged QT interval;
 - Brugada syndrome;
 - arrhythmogenic right ventricular cardiomyopathy;
- Symptomatic orthostatic hypotension diagnosed by standing BP measurement;
- Nonsyncopal loss of consciousness (eg, epilepsy, psychiatric, metabolic, drop-attack, cerebral transient ischemic attack, intoxication, cataplexy).
- Symptomatic cardio-inhibitory carotid sinus hypersensitivity.

